The purpose of this study is to prospectively compare preoperative (neoadjuvant) SRS/SRT to postoperative (adjuvant) SRS/SRT in patients undergoing surgical resection for brain metastases.

Hypothesis, Objectives, and Outcomes

We hypothesize that neoadjuvant SRS/SRT prior to surgical resection of brain metastases will result in improved freedom from Central Nervous System (CNS) events when compared to adjuvant SRS/SRT after surgical resection.

Primary Objectives

- Our primary objectives are: (1) to determine the *Time to a Central Nervous System* (*CNS*) *Composite Event* (*CE*) in subjects who receive either neoadjuvant (preoperative) SRS/SRT or adjuvant (post-operative) SRS/SRT for their brain metastases, and (2) to compare the two treatment arms for evidence of improved Time to a CNS CE among subjects who received neoadjuvant SRS/SRT.
 - A CNS CE will consist of one of the following three events: Local Recurrence (LR) of the treated lesions, symptomatic radiation necrosis (SRN) to the treated lesions, or development of leptomeningeal disease (LMD). See below for detailed definitions of LR, SRN, and LMD.
 - Time to a CNS CE, the primary outcome, will be measured as the time from the date of randomization to the date of a documented LR, SRN, or LMD, whichever occurs first.
 - Death before occurrence of a CNS CE will be treated as a competing risk. Study participants who are alive and have yet to experience a CNS CE at their last evaluation will be right-censored for Time to CNS CE on the date of their last evaluation.

Secondary Objectives related to the Primary Objective. Some of our secondary objectives include (a) determining in each study subject the *secondary outcomes* listed below, and (b) comparing the treatment arms for evidence of improvements in these secondary outcomes.

- Index lesion local recurrence (ILLR), a component of CNS CE, will be defined as the development of new nodular contrast enhancement in the surgical bed compared with the immediate postoperative MRI.
- Non-index lesion LR, also a component of CNS CE, will be defined as an increase of more than 25% in the size of any treated non-resected brain lesion.

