 - Time to LR, a secondary outcome, will be measured as the time from the date of randomization to the date of documented occurrence of the LR. Death before occurrence of LR will be treated as a competing risk. Study subjects who are alive and free of LR at their last evaluation will be rightcensored for Time to LR on the date of their last evaluation.
- Leptomeningeal disease (LMD), a component of CNS CE, will be diagnosed by imaging results consistent with this condition (either local or diffuse leptomeningeal disease) or by examination of spinal fluid positive for malignant cells.

- Time to LMD, a secondary outcome, will be measured as the time from the date of randomization to the date of documented first occurrence of the LMD. Death before occurrence of LMD will be treated as a competing risk. Study subjects who are alive and free of LMD at their last evaluation will be right-censored for Time to LMD on the date of their last evaluation.
- Radiation Necrosis (RN) of the treated lesions. If radiation necrosis is suspected based on imaging criteria (progression of contrast-enhancing mass that is associated with reduced perfusion on dynamic MRI, increased T2 flair/T2 hyperintensive signals within previous radiation treatment fields for the index lesion), then follow-up MRI imaging (with MRS, PET/SPECT as optional) will be obtained 4-6 weeks later to confirm the diagnosis of RN. The Time to RN will be back-dated to the initial imaging-findings date if the diagnosis of RN is confirmed by the follow-up imaging.
 - Stratified by surgical site versus non-surgical sites and the use of targeted therapy, cytotoxic chemotherapy, or immunotherapy
- Symptomatic Radiation Necrosis (SRN), a component of CNS CE, will be documented radiation necrosis of the treated lesions (see above) that is accompanied by symptoms (headaches, nausea, vomiting, or other neurologic symptoms).
 - Time to SRN, a secondary outcome, will be measured as the time from the date of randomization to the date of documented occurrence of the SRN. Death before occurrence of the SRN will be treated as a competing risk. Study subjects who are alive and free of SRN at their last evaluation will be right-censored for Time to SRN on the date of their last evaluation.

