Other Secondary Objectives include determining the other secondary outcomes described below, and comparing treatment arms for improvements with neoadjuvant SRS/SRT in (a) the rates of secondary yes/no outcomes such as Local Control, or (b) the 6-month, 12-month, 18-month, month rates of secondary time-to-event outcomes such as Duration of Local Control:

- Local Control.
 - Local Control will be defined as Complete Response [CR], Partial Response [PR], or Stable Disease [SD] of the index lesion resulting from the assigned treatment. It will be determined at the first evaluation following successful completion of either neoadjuvant or adjuvant SRS/SRT of all metastatic lesions and surgical resection of the index lesion.
 - Stratified by GTR or STR, piecemeal vs en bloc resection

- Treatment Failure will be defined either as Progressive Disease [PD] during the assigned treatment, or as the absence of Local Control at the first evaluation following successful completion of the assigned treatment.
- Duration of Local Control (DLC) will be measured as the time from the date when Local Control is first documented to the date when:
 - the treated lesions show documented evidence of LR or PD, or
 - the patient undergoes whole-brain radiotherapy, repeat SRS, repeat surgical intervention
- Time to distant in-brain failure.
 - Distant in-brain failure (DiBF) will be defined as the occurrence of any new parenchymal lesion outside of the planning target volume.
 - Time to DiBF will be measured as the time from the date of randomization to the date of occurrence of the DiBF. Death before occurrence of DiBF will be treated as a competing risk. Study subjects who are alive and free of DiBF at their last evaluation will be right-censored for Time to DiBF on the date of their last evaluation.
- Overall survival.
 - Overall survival (OS) will be measured as the time from the randomization date to the date of death for any reason. Study participants who are still alive at last follow-up will be right-censored for OS on the date of their last follow-up.
- Time to systemic therapy.
 - Time to initiation or re-initiation of systemic therapy will be measured as the time from the date when the assigned treatment (neoadjuvant versus adjuvant SRS/SRT) is successfully completed to the date when the systemic therapy is initiated or re-initiated.

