Data Safety Monitoring Plan: The study will be monitored by the investigators to ensure that the rights and well-being of human subjects are protected, that the data are accurate, complete and verifiable from source documents and that the trial is conducted in compliance with currently approved protocol/amendments. The PI and sub-Investigators will review study conduct on an ongoing basis. The PI will assure that all protocol deviations, AEs, and SAEs are reported to the IRB according to the applicable regulatory requirements.

Specimen Handling and Storage

Tumor specimens will be collected from surgical resection and stored by the Department of Pathology and kept as part of standard of care. No samples will be collected specifically for use in this study at this time.

Data Analysis

Statistical analysis plan

Patient characteristics will include patient demographics, disease characteristics of the primary tumor, and relevant characteristics (number, location, size, etc.) of the brain metastases being treated. Patient characteristics will be summarized by treatment arm with medians, quartiles, and ranges for numeric characteristics, or with numbers and percentages for category characteristics. Each characteristic then will be assessed for imbalance between treatment arms with Wilcoxon's rank-sum test for numeric characteristics. The imbalance assessments will consist of 2-sided tests that employ the standard α =0.05 significance level.

Time to a CNS CE, the primary outcome, will be visualized with Cumulative Incidence (CI) curves computed using Kaplan-Meier methodology, summarized by treatment group as CI proportions at 6, 12, and 18 months, and compared for difference using the Fine and Gray model for equality of CI functions when death before a CNS CE is treated as a competing risk. Times to each of the individual CNS events (LR, SRN, LMD, DiBF, and WBRT) will be analyzed the same way, except that each Fine and Gray model will have the competing risk be death before the individual event being analyzed. Overall survival will be visualized using standard Kaplan-Meier curves and compared for differences via the log-rank test. Because this is a pilot study, all time-to-event outcomes will be compared for evidence of improvement on the pre-operative SRS/SRT arm using 1-sided tests that employ an α =0.10 significance level.

Sample size, power, and study duration

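### Cumulative incidence curves and 6-, 12- and 18-month proportions are to be computed by Kaplan-Meier although death is a competing risk; with deaths censored in the usual way, each arm's proportion is overstated

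*Combined protocol and SAP*

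**What the plan says.** The Statistical analysis plan section (under Data Analysis) displays the primary outcome with "Cumulative Incidence (CI) curves computed using Kaplan-Meier methodology, summarized by treatment group as CI proportions at 6, 12, and 18 months". In the same sentence the arms are "compared for difference using the Fine and Gray model for equality of CI functions", with death before a CNS CE as the competing risk. The next sentence applies this analysis to LR, SRN, LMD, DiBF and WBRT, each with death before the event in question as the competing risk. Overall survival gets standard Kaplan-Meier curves and a log-rank test.

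The endpoint definitions handle death consistently:

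- **CNS CE** (Primary Objectives): "Death before occurrence of a CNS CE will be treated as a competing risk". Censoring is confined to the living: "Study participants who are alive and have yet to experience a CNS CE at their last evaluation will be right-censored".
- **LR, LMD and SRN** (Secondary Objectives related to the Primary Objective): "Death before occurrence of LR will be treated as a competing risk"; "Death before occurrence of LMD will be treated as a competing risk"; "Death before occurrence of the SRN will be treated as a competing risk".
- **DiBF** (Other Secondary Objectives): "Death before occurrence of DiBF will be treated as a competing risk".

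No section names an estimator such as Aalen-Johansen for the curves, or says that participants who die stay in the Kaplan-Meier risk set.

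**The concern.** Kaplan-Meier has two outcomes for a participant, event or censored. Used in the ordinary way for time to CNS CE, it censors a participant at death, as though that person could still have had the event later. One minus Kaplan-Meier (1-KM) then estimates the incidence that would be seen if nobody died first. The endpoint definition and the Fine and Gray comparison concern something else: the proportion of participants who actually have a CNS CE, given that some die before one can occur.

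Primary objective (1) is to determine Time to CNS CE in each arm. The curves and landmark proportions are the only descriptive summary planned for it. Inflated values would misstate the absolute risk in each arm, would not match the reported test, and could mislead anyone using this pilot to plan a later trial.

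**Working it through.** **Direction.** Let h(u) be the CNS CE hazard, S(u) the Kaplan-Meier curve with deaths censored, and G(u) the corresponding curve for death before a CNS CE.

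- 1-KM at time t is the integral of h(u)S(u) from 0 to t.
- The competing-risks cumulative incidence (CIF) is the integral of h(u)S(u)G(u).

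Because G(u) never exceeds 1, 1-KM is never below the CIF, and it is above it once deaths precede later events. This does not depend on any assumed rate.

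**Inputs for the size** (Sample size, power, and study duration): CNS CE rate 25.0% per year post-operative and 12.5% pre-operative; death before CNS CE 32% per year in both arms; 52 participants per arm; 3 years' accrual and 1.5 years' minimum follow-up. Constant hazards are assumed.

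**The plan's own figures.** The plan states no cumulative incidence proportion. The figures available to reproduce are 80.7% power and 26.0 expected events. With the stated accrual and follow-up, no reading tried gave both:

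| Event rate / death rate read as | Expected events | Power, Lakatos to Schoenfeld |
|---|---|---|
| hazard / hazard | 28.6 | 70.5% to 71.7% |
| annual proportion / annual proportion | 29.0 | 77.0% to 78.4% |
| annual proportion / hazard | 31.1 | 79.2% to 80.5% |
| hazard / annual proportion | 26.6 | 68.2% to 69.4% |

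This is a separate matter. Here it means only that the plan does not show how its rates were entered, so the sizes below are illustrative.

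**Rates read as hazards.** With d = 0.32 and h = 0.25 (post-operative) or 0.125 (pre-operative):

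- 1-KM = 1 - exp(-h t)
- CIF = h/(h+d) × [1 - exp(-(h+d) t)]

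At t = 1.5 years:

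- Post-operative: 1-KM = 1 - exp(-0.375) = 31.3%; CIF = (0.25/0.57) × [1 - exp(-0.855)] = 25.2%.
- Pre-operative: 1-KM = 1 - exp(-0.1875) = 17.1%; CIF = (0.125/0.445) × [1 - exp(-0.6675)] = 13.7%.

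| Month | Post-op 1-KM / CIF | Pre-op 1-KM / CIF | Difference 1-KM / CIF (points) | Excess in difference |
|---|---|---|---|---|
| 6 | 11.8% / 10.9% | 6.1% / 5.6% | 5.7 / 5.3 | 0.4 |
| 12 | 22.1% / 19.1% | 11.8% / 10.1% | 10.4 / 9.0 | 1.4 |
| 18 | 31.3% / 25.2% | 17.1% / 13.7% | 14.2 / 11.5 | 2.6 |

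Differences and excesses are taken before rounding. At 18 months the excess is 6.1 points post-operative and 3.4 pre-operative, or 24-25% in relative terms. The ratio of the arms hardly moves (0.547 against 0.543). The standard error of the 18-month difference is about sqrt(0.252×0.748/52 + 0.137×0.863/52) = 7.7 points, so the excess of 2.6 points is about one third of it.

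**Rates read as annual proportions.** With h = -ln(0.75) or -ln(0.875) and d = -ln(0.68), the 18-month values are 35.0% against 27.2% post-operative and 18.2% against 13.9% pre-operative. The difference is 16.9 against 13.2 points, an excess of 3.6 before rounding.

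**Range.** Over the four readings the 18-month overstatement is 6.1-7.9 points post-operative and 3.4-4.2 points pre-operative, about 24-30% relative.

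**Number of deaths involved.** Expected deaths before a CNS CE by 18 months (hazard reading) are 52 × d/(h+d) × [1 - exp(-(h+d) × 1.5)] = 16.8 post-operative and 18.2 pre-operative, about a third of each arm.

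**Simulation.** 20,000 trials of 52 per arm were generated with exponential times (hazard reading), administrative censoring uniform on 1.5 to 4.5 years and no other loss to follow-up. The mean 18-month estimates, post-/pre-operative, were 31.3%/17.1% with deaths censored, 25.2%/13.7% with deaths kept in the risk set, and 25.2%/13.7% by Aalen-Johansen.

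**The case against.** The strongest reply is that the plan never says deaths will be censored. Its definitions censor only participants who are alive and event-free, it labels the curves cumulative incidence, it tests cumulative incidence functions in the same sentence, and it keeps the standard Kaplan-Meier label for overall survival. Taken together, this may be a competing-risks curve described loosely. Kaplan-Meier with deaths retained is also unbiased at 18 months in the simulation, so one clarifying clause might be enough. This stands as far as intent goes, and it is why every size given here is conditional. It does not settle the matter: the plan names a method whose ordinary use is the biased one, and nothing in the text rules that use out.

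It is also fair that the consequences are limited. The formal test is unaffected, the ratio of the arms barely changes, and no decision rule rests on a landmark proportion. These points bear on how serious the problem is, not on whether it exists.

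For WBRT, the outcome definition (time to subsequent brain treatment) runs from completion of assigned treatment and gives no rule for death or censoring. The analysis section, however, itself places WBRT under the same method with death as the competing risk, so the point reaches it too.

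**Conclusion.** The concern holds and should be fixed. The estimator named for the primary outcome's curves and proportions does not, in its usual form, estimate the quantity that the plan defines and tests. The direction of error in each arm is certain if deaths are censored. The size, about 24-30% relative at 18 months, rests on constant hazards and on the planning rates. The direction of bias in the arm difference depends on the death rates in the two arms; with equal rates, as the sample-size section assumes, the difference is overstated. The documents give no rates for LR, SRN, LMD, DiBF or WBRT, so the size for those outcomes cannot be stated. The problem is confined to description: the Fine and Gray test, the alpha level and the sample size do not change.

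**What to change.** In the Statistical analysis plan section, replace the reference to Kaplan-Meier methodology for these curves with wording such as: *estimated by the Aalen-Johansen (competing-risks) cumulative incidence estimator, with death before the event as the competing event*. Apply it to Time to CNS CE and to LR, SRN, LMD, DiBF and WBRT, for both the curves and the 6-, 12- and 18-month proportions. Leave Kaplan-Meier for overall survival as it is. Nothing is proposed here for outcomes that this part of the plan does not cover.

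The cost is a change of wording. No extra participants or data are needed, because dates of death are already required for overall survival. If the authors meant a competing-risks estimator all along, the edit simply records it.

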Work by Patchell et al. demonstrated that whole brain radiotherapy (WBRT) after surgical resection of a single brain metastasis reduced the rate of recurrence at the site of the original metastasis and at other sites of the brain.³ It also decreased the likelihood of death from neurologic causes. However, WBRT is not without side effects; there is particular concern with the long-term neurocognitive effects of treatment.

As a result, postoperative stereotactic radiosurgery (SRS) and less than 5 fractions of stereotactic radiation therapy (SRT) has become increasingly popular. SRS/SRT delivers high doses of radiotherapy via multiple beam angles and highly conformal planning techniques to the target, sparing normal brain tissue. A randomized trial by Brown et al. found that postoperative SRS had similar overall survival (OS) when compared to postoperative WBRT (median OS of 12.2 months vs. 11.6 months, respectively [p = 0.70]) but had lower rates of cognitive deterioration (52% vs 85% [p<0.001]).⁴ When compared to observation after surgery, a separate trial demonstrated improved local control with postoperative SRS.⁵

There is growing interest in whether SRS/SRT delivery for brain metastases can be transitioned to the preoperative (or neoadjuvant) setting. Radiotherapy has been used neoadjuvantly for many disease sites, including rectal, pancreatic, esophageal and sarcomatous cancers. Neoadjuvant timing for brain metastases offers several potential benefits. First, target delineation is much simpler preoperatively compared to postoperatively (where the tumor bed is large and can change over time). This smaller treatment volume may also decrease the risk of toxicity or radiation necrosis.

Neoadjuvant radiotherapy may also help with disease control. Local recurrence remain somewhat high (~44%) for tumors greater than 3cm in diameter,⁵ likely related to tumor spill at the time of surgery. In addition, there is concern for leptomeningeal spread after surgery due to surgical tract seeding into the meningeal space. Preoperative SRS or SRT to the tumor may serve as a way to, in effect, "sterilize" the tumor site and reduce the risk of local recurrence and leptomeningeal spread. Series have suggested that neoadjuvant SRS or SRT results in lower rates of leptomeningeal disease when compared to postoperative SRS or SRT.

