- Time to subsequent brain treatment, including whole-brain radiotherapy (WBRT), will be measured as the time from the date when the assigned treatment is successfully completed to the date when the WBRT or other subsequent treatment is initiated.
- Radiation/Surgery toxicity
 - o The rate of symptomatic (≥grade 2) radiation/surgery toxicity

 Incidence of adverse events as graded by the National Cancer Institute (NCI) Common Terminology Criteria for Adverse Events (CTCAE) version 5.0

Study Design and Procedures

Design: This pilot study is a randomized, open-label, 2-arm active-controlled phase II clinical trial conducted at a single study site (UAMS) located in central Arkansas. Prospective enrollees will be screened based on the inclusion/exclusion criteria listed below in the *Study Population* section. Study-eligible candidates who agree to participate will be assigned by randomization to one of the 2 treatment arms shown in the table below:

Treatment Arm	Intervention/treatment
Experimental: Arm I (pre-operative SRS/SRT)	Radiation: Stereotactic Radiosurgery Undergo SRS/SRT Other Names:
Patients undergo SRS or SRT within 15 days of randomization followed by surgery within 15 days of radiation completion. Patients may undergo	Stereotactic External Beam Irradiation
	 stereotactic external-beam radiation therapy
additional SRS or SRT if disease returns after treatment.	stereotactic radiation therapy
	Stereotactic Radiotherapy
	 stereotaxic radiation therapy
	 stereotaxic radiosurgery
Active Comparator: Arm II (post- operative SRS/SRT) Patients undergo surgery within 15 days of randomization followed by standard-of-care SRS or SRT within 30	Undergo SRS/SRT Other Names: • Stereotactic External Beam Irradiation
	 stereotactic external-beam radiation therapy
days of surgery. Patients may undergo additional SRS or SRT if disease	stereotactic radiation therapy
returns after treatment.	Stereotactic Radiotherapy
	 stereotaxic radiation therapy
	stereotaxic radiosurgery

The dose, volume and fractionation of radiotherapy will be at the discretion of the radiation oncologist at the time of SRS/SRT depending on the size, location, and proximity to critical structures. Before treatment commences, each study participant will be stratified according to two stratification factors:

- Size of Index Lesion (<3 cm versus ≥3 cm)
- Number of Brain Metastases (4 or fewer versus 5 or more)

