These stratification factors will be used during the randomization procedure to assure that the treatment arms will be well-balanced with respect to index-lesion size and brainmetastasis number.

On-study Plan: After first signing the IRB-approved Informed Consent form, and after then being stratified according to size of index lesion and number of brain metastases, study participants will be registered and assigned a study number by a clinical research associate (CRA) or Study Coordinator.

Randomization and Treatment Allocation: After the study participant's eligibility has been confirmed, and after the participant has been stratified (see above) and registered in the Research Participant Registration System (RPRS), the study coordinator will do two things. First, the study coordinator will use the RPRS to assign the participant to one of the four possible strata defined by the stratification factors. Then the study coordinator will use the RPRS to randomize the participant in a 1:1 allocation ratio to either Arm I (pre-operative SRS/SRT) or Arm II (post-operative SRS/SRT). The randomizations will be balanced 1:1 on treatment arms within each stratum by using a permuted-blocks approach. Study participants will receive either pre-operative or post-operative SRS/SRT depending on the study arm to which they are randomized. Accordingly the two study arms will follow the treatment schedules shown in the table.

Sample Collection: The extent (gross total or subtotal resection) and technique for surgery (en bloc or piecemeal) will be determined by the neurosurgeon. The pathological specimen will be analyzed and stored by the Department Pathology per standard operating procedure for resected brain tumor specimens.

Follow-up: After completion of radiotherapy and surgery, study subjects will be followed by Brain MRI every 2-3 months for the first year and then every 4-6 months indefinitely (in accordance with National Comprehensive Cancer Network [NCCN] guidelines). Imaging and follow-up can be done sooner than these specified times if clinically indicated. MRI's will be included in study results up to 18 months.

Study Population

Ages Eligible for Study: Sexes Eligible for Study: Accepts Healthy Volunteers: Estimated Enrollment 18 Years and older (Adult, Older Adult)AllNo104 (we anticipate consenting 120 in order to reach this goal)

Inclusion Criteria

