Sample-size calculations are informed by results from Patel et al.'s retrospective study.⁶ Based on their results, we expect that the post-operative SRS/SRT arm will have an average CNS CE rate of approximately 25% per year, accompanied by an average competing-risks rate of approximately 32% per year (where the competing risk is death before the CNS CE). Sample-size calculations are also informed by the fact that UAMS typically sees approximately 50 patients per year who should meet this study's eligibility requirements.

To meet its objectives, our randomized Phase II pilot study of pre-operative SRS/SRT versus post-operative SRS/SRT needs to have >80% power to detect a 50% decrease in the rate of CNS CE on the pre-operative SRS/SRT arm using a 1-sided test at 10% alpha. The power of tests under the Fine and Gray competing-risks model is well-approximated by the power of log-rank tests calculated with the competing-risk rate represented as non-zero dropout rates on each study arm. To calculate power of 1-sided log-rank tests at 10% alpha, we implement the following assumptions in PASS 16 software⁹:

- Accrual duration will be three years while minimum follow-up will be 1.5 years, leading to a total study duration of 4.5 years.
- The post-operative SRS/SRT arm will have a CNS CE rate that averages 25.0% per year.
- The pre-operative SRS/SRT arm will have a CNS CE rate that averages 12.5% per year, or half the rate on the post-operative SRS/SRT arm.
- Both arms will have a dropout rate of 32% per year due to the competing risk.
- The crossover rate from one arm to the other will be zero on both arms.
- Sample sizes will be equal on both arms.

Under these assumptions, a sample size of 52 subjects per treatment arm (a total of 104 subjects) is calculated to provide the 1-sided log-rank test (and thus the equivalent Fine and Gray test) with 80.7% power at 10% alpha to detect a 50% reduction in the CNS CE rate with pre-operative SRS/SRT relative to the CNS CE rate with post-operative SRS/SRT. Under the same assumptions, the number of CNS CE's is projected to reach expected values of 8.6 with pre-operative SRS/SRT and 17.4 with post-operative SRS/SRT for a total expected value of 26.0 by the end of the study.

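### The primary Fine and Gray test leaves out the two factors used to stratify randomization; accounting for them is a cheap, low-priority gain of about 0 to 2 points of power, and the planned test remains valid

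*Combined protocol and SAP*

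**What the plan says.** Study Design and Procedures defines two binary stratification factors: index-lesion size, cut at 3 cm, and number of brain metastases, cut between 4 and 5. It gives them a role in the design: "These stratification factors will be used during the randomization procedure", so that the arms are balanced on them. Randomization and Treatment Allocation adds that "The randomizations will be balanced 1:1 on treatment arms within each stratum by using a permuted-blocks approach", which gives four strata.

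The Statistical analysis plan under Data Analysis says the primary outcome will be "compared for difference using the Fine and Gray model for equality of CI functions", with death before a CNS CE as the competing risk, in a one-sided test at alpha 0.10. It names no stratum or covariate. Sample size, power, and study duration bases power on a log-rank test with no stratification, with death entered as dropout ("Both arms will have a dropout rate of 32% per year due to the competing risk"), and projects CNS CEs "for a total expected value of 26.0 by the end of the study".

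Two outcome definitions carry a line beginning with the word stratified (radiation necrosis and Local Control), but these use other variables and do not concern the primary test.

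**The concern.** When arms are balanced on a factor that also predicts the outcome, the treatment comparison varies less from trial to trial than an arm-only test assumes. The test then overstates its variance, rejects a little less often than its nominal level under the null, and gives up some power. With 26.0 events expected and a requirement of more than 80% power, information that is already recorded should not be discarded without a reason.

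There is also a small pre-specification gap. Fine and Gray is a regression model, and the plan does not say whether covariates enter it. The plan tests baseline imbalance but does not say what follows from an imbalance. The trial is open-label, so the choice is better fixed before data are seen.

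**Working it through.** **1. The plan's own figures.** Inputs from Sample size, power, and study duration: 52 per arm, CNS CE rates 0.25 and 0.125 per year, competing rate 0.32, 3 years' accrual, 1.5 years' minimum follow-up, one-sided alpha 0.10. Take the rates as hazards, with total hazard L = h + 0.32. The event probability is (h/L) × [1 − (e^(−1.5L) − e^(−4.5L))/(3L)].

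- Post-operative: L = 0.57; 0.4386 × 0.7963 = 0.3492; × 52 = 18.16 events.
- Pre-operative: L = 0.445; 0.2809 × 0.7169 = 0.2014; × 52 = 10.47 events.
- Total 28.6. Schoenfeld power: Φ(√(28.63/4) × ln 2 − 1.2816) = Φ(1.854 − 1.282) = 71.7%. With the plan's 26.0 events it is Φ(1.767 − 1.282) = 68.6%.

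The stated 80.7% with 26.0 events is not reproduced. That is a separate question. Here only differences between tests matter, not absolute power.

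**2. Simulation.** 104 patients, two binary factors, permuted blocks of 4 within four strata, hazards as above (0.25 in both arms for alpha), administrative censoring only. Block size, factor prevalences, factor hazard ratios (HRs) and effects on death are all assumptions. The arm-only score test is compared with a Wald test adjusted for both factors as main effects. With each factor split 50:50 there were 40,000 trials per cell. HRs are given as size, number, and act on CNS CE only:

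| HRs | alpha, arm-only / adjusted | power, arm-only / adjusted | gain (points) |
|---|---|---|---|
| 1.5, 1.5 | 9.9% / 10.2% | 66.5% / 66.9% | +0.4 |
| 2, 1.5 | 9.5% / 10.1% | 65.0% / 66.0% | +1.0 |
| 3, 2 | 8.8% / 10.3% | 61.1% / 63.9% | +2.8 |

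With non-prognostic factors the difference is +0.1, which is no real gain. The Monte Carlo SE is about 0.15-0.21 points on alpha and 0.06-0.15 on the power differences.

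**3. Effects on death and prevalence.** Fine and Gray works on cumulative incidence, which depends on the death hazard too. If the same HRs also act on death, the gains fall to +0.1, +0.5 and +1.0. CNS CE HRs of 3, 2 with death HRs of 1.5, 2 give +1.6. If only 20% have 5 or more metastases (20,000 trials per cell), the gains are +0.6, +1.0 and +2.6 without a death effect and 0.0, +0.3 and +1.0 with equal death effects.

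**4. Allowing for alpha.** Part of each gain arises because the adjusted test rejects slightly more than 10% under the null. Shift its critical value to a true 10% by normal approximation: corrected power = Φ(Φ⁻¹(power) − [1.2816 − z at actual alpha]).

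- HRs 1.5, 1.5: Φ(0.4372 − 0.0113) = 66.5%; gain 66.5 − 66.5 = 0.0.
- HRs 2, 1.5: Φ(0.4125 − 0.0057) = 65.8%; gain 65.8 − 65.0 = +0.8.
- HRs 3, 2: Φ(0.3558 − 0.0169) = 63.3%; gain 63.3 − 61.1 = +2.2.

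A separate simulation (12,000 trials per cell) gave alpha 9.7% / 10.3% and power 64.9% / 65.9% at HRs 2, 1.5, and alpha 9.0% / 10.5% and power 61.5% / 64.3% at HRs 3, 2. Held to a true 10% alpha, its gains were about +0.3 and +1.9. The range is therefore about 0-2 points for HRs up to 3 and 2.

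**5. Covariates or strata.** In the separate simulation of step 4, the four-stratum stratified test had alpha 9.9-10.4% and power within about 0.5 points of the adjusted Wald test. In a further set (about 8,000 trials per cell) its alpha was 9.5-10.7%, with gains over the arm-only test of +0.6 to +0.9 points at HR 2 on both factors and +3.0 to +3.5 at HR 3 on both. Sparse strata do occur: the chance that at least one stratum has 2 or fewer events was 25% (HRs 2, 1.5) to 53% (3, 2) without a death effect, and 54-73% if 20% have 5 or more metastases.

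**6. Change in what is estimated.** From a simulated cohort of 400,000 per setting without a death effect, the subdistribution HR is 0.530 marginal and 0.523 conditional at HRs 2, 1.5, and 0.544 and 0.526 at HRs 3, 2.

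**The case against.** The best defence is that the plan is coherent as it stands. Stratification is given a balancing purpose, the analysis shows marginal cumulative incidence by arm and tests those curves, and power rests on an unadjusted log-rank test. An adjusted primary test makes the arm effect conditional and moves it away from both. The arm-only test errs on the safe side, while the adjusted Wald test ran at 9.9-10.6% over 16 settings. It also fits three parameters to about 26 events.

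Nor do the documents show that the factors are prognostic. The background text says "Local recurrence remain somewhat high (~44%) for tumors greater than 3cm in diameter", but that concerns one component of the composite and gives no figure for smaller tumors. Nothing supports number of metastases.

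All of this stands, and it keeps the point small. It does not remove it: the trial already randomizes by these groups, and analyzing by them is a better use of the same data at almost no cost.

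A reader might infer that a four-stratum stratified test must be avoided because strata will be sparse. The results do not support that. A sparse stratum adds little information but does not invalidate the test, and its alpha and power were close to those of the covariate form.

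**Conclusion.** The omission is real and its consequence is minor. Under the assumed settings, with factor HRs up to 3 and 2, the arm-only test has one-sided alpha of about 9-10% and loses about 0-2 points of power (0-3 before the alpha allowance). The loss is close to zero if the factors are weak or not prognostic, and smaller if they also raise the death hazard. Only the extreme case of HR 3 on both factors exceeds the range, at 3.0-3.5 points for the stratified test.

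A reader might infer that ignoring the strata inflates type I error or invalidates the primary test. It does neither; the departure is towards conservatism. Nor does this point explain the stated 80.7% power. The size rests on assumed prognostic strength, prevalence and block size, so confidence in any single figure is moderate. Component events and overall survival were not simulated, and nothing is claimed about them.

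**What to change.** As a low-priority improvement for the primary outcome only, state in the Statistical analysis plan that the primary Fine and Gray test accounts for index-lesion size and number of metastases as recorded at randomization. Choose one form in advance:

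- main-effect covariates, with the arm effect tested by a one-sided Wald test at alpha 0.10; or
- a stratified test over the four strata, with a stated rule for sparse strata, given about 26 events in all.

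Report the arm-only result as a sensitivity analysis beside the planned cumulative incidence curves. Add a sentence saying that the reported arm effect is conditional on the two factors.

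The cost is a few sentences, with no change to sample size or data collection. The downsides should be accepted openly: the test no longer matches the unadjusted log-rank power basis exactly, its actual alpha may sit a few tenths of a point above 10%, and there may be no gain. If the sponsor prefers the arm-only test, saying that this is intended would at least close the pre-specification gap.
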